### **7.2.2 Post-Baseline**

The visit window for ECR is defined in Section 6.1. Clinical efficacy and safety analyses will utilize the data obtained on the scheduled visit (ie, nominal visit will be utilized). When a nominal visit assessment is unavailable, an unscheduled assessment may be utilized as described in Appendix D.

See [Appendix A](#) for a complete description on the timing of the safety assessments. See Appendix D for a summary of visit window definitions for the safety assessments.

### **7.2.3 Unscheduled Assessments**

If no scheduled visit was done, but an unscheduled safety assessment was done in the window of the scheduled assessment (for the specific safety parameter), the unscheduled assessment should be used as described in Appendix D. If more than 1 measurement is taken during the visit window (a scheduled visit and an unscheduled visit), the value taken on the scheduled visit will be utilized. If more than one unscheduled assessment is completed in the visit window of the scheduled assessment (and no scheduled assessment), the earliest should be used. All unscheduled visits not satisfying the analysis visit condition as described in Appendix D will be referred to as “Unscheduled” as their analysis visit designation. For overall worst post-baseline analyses (i.e. minimum, maximum, highest, lowest, any post-baseline, and PCS), all assessments including those obtained on unscheduled (i.e. analysis visit “Unscheduled”) and scheduled visits (e.g., analysis visits “Baseline”, “Day 1”, “Day 4”, “TOC”, “EOT” and “LFU”) will be included. See Section 8.7.2 for a discussion of when to use central and local safety laboratory values.

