- Receipt within 7 days before enrollment of Class IA or Class III anti-arrhythmic medication or, in the opinion of the Investigator, subject may require such medication during the study. (Class 1A: Quinidine, Procainamide, Disopyramide; Class III: Amiodarone, Dofetilide, Ibutilide, Sotalol)
- Receipt within 7 days before enrollment of medication that has the potential of prolonging the QT interval or, in the opinion of the Investigator, subject may require such medication during the study (see Appendix 5).
- 8. Be receiving a strong p-glycoprotein inhibitor or a strong CYP3A inducer or inhibitor (see Appendix 4).
- 9. Have a history of tendon disease/disorder, myasthenia gravis, or known or suspected central nervous system (CNS) disorders (severe cerebrovascular arteriosclerosis, epilepsy, or other risk factors that may predispose to seizures).
- 10. Have a history of any hypersensitivity or allergic reaction to any fluoroquinolone, or any drug in the pleuromutilin class (i.e., retapamulin).
- 11. Have severely impaired renal function, defined as estimated creatinine clearance (CrCl) ≤30 mL/min as calculated by the Cockcroft-Gault formula.
- 12. Have evidence of significant hepatic, hematologic, or immunologic disease including any of the following:
  - Known acute hepatitis, including acute viral hepatitis.
  - Aspartate aminotransferase (AST) or alanine aminotransferase (ALT) level > 5 times the upper limit of normal (ULN),
  - Total bilirubin > 3 times the ULN (unless known Gilbert's disease).
  - Aspartate aminotransferase (AST) or alanine aminotransferase (ALT) level > 3 times the upper limit of normal (ULN) and total bilirubin > 2 times the ULN.
  - History of cirrhosis of the liver.
  - Manifestation of end-stage liver disease, such as ascites or hepatic encephalopathy.
  - Current or anticipated neutropenia (<500 neutrophils/mm^3).
  - Thrombocytopenia (<50,000 platelets/mm^3).
  - Known infection with human immunodeficiency virus and a CD4 count < 200/mm^3.
- 13. Have known severe immunosuppression, including but not limited to receipt of corticosteroid therapy (≥20 mg of prednisone/day or equivalent for >4 weeks) within the previous 8 weeks; solid organ or bone marrow transplantation within the previous 12 months; or currently receiving cytotoxic chemotherapy.

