# 9.7 Safety Analysis

Safety will be evaluated in the Safety Analysis Set by presenting summaries of AEs, routine clinical laboratory evaluations, ECGs, and vital signs in the 2 treatment groups. Subjects who receive the wrong study drug for their entire course of treatment will be analyzed in the group based on the drug received.

Summary tables will be provided for all TEAEs. A TEAE is defined as an AE with a start date and time on or after the first dose of study drug. Adverse events will be coded using the Medical Dictionary for Regulatory Activities (MedDRA®). The number and percentage of subjects with TEAEs will be tabulated by system organ class (SOC) and MedDRA Preferred Term for each treatment group and by severity and relationship to treatment.

Adverse events leading to premature discontinuation from the study drug and serious TEAEs will be presented either in a table or a listing.

Change from baseline to each scheduled evaluation and the overall worst post-baseline in clinical laboratory variables will be summarized by treatment group. The number and percent of subjects with treatment-emergent potentially clinically significant (PCS) laboratory values will be tabulated for each treatment group. Treatment-emergent PCS laboratory tests are those in which the Baseline value is not PCS and the post-baseline value is PCS. PCS will be defined based on the pre-specified criteria outlined in the SAP.

Change from baseline to each scheduled evaluation and the overall worst post-baseline for RR interval, PR interval, QRS interval, QT interval, and QT interval corrected with Fridericia from the ECG will be summarized for each treatment group with the mean, standard deviation, minimum value, and maximum value. The triplicate values will be averaged for each subject before analysis. An outlier analysis will also be provided based on the worst post-baseline value.

Descriptive statistics of vital signs and the change from baseline to each scheduled evaluation will be summarized by treatment group at each study visit and the worst overall post-baseline. The number and percent of subjects with treatment-emergent PCS values will be tabulated for each treatment group.

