## 7.2 Visit Windows

### 7.2.1 Baseline

Unless otherwise stated below, baseline is defined as the last measurement prior to the first dose of study drug.

- For microbiological pathogen determination, baseline is defined as the 24-hour period prior to the administration of the first dose of study drug and the 24 hours after the first dose of study drug. A pathogen identified from a respiratory (pleural fluid, bronchoalveolar lavage (BAL), sputum), blood for culture, urine, nasopharyngeal or oropharyngeal specimen collected at baseline is considered a baseline pathogen. An atypical pathogen identified by serology is considered a baseline pathogen if the baseline

sample is collected in the 24-hour period prior to or the 24 hours after the administration of the first dose of study drug.

- For vital signs, baseline is defined as the Screening assessment (since time of assessment is not captured) as long as the date of collection is on or before the date of first dose of study drug.
- For ECGs, baseline is defined as the mean of the triplicates (or duplicate or single, if a triplicate is not obtained) from the last assessment prior to the first dose of study drug, including scheduled and unscheduled visits.
- If no study drug is received, baseline is defined as the measurement taken at the Screening Visit (ie, prior to the randomization date/time)

Study Day 1 is defined as the first calendar day of study drug administration (or the date of randomization if no study drug was received). The calendar day prior to the first dose of study drug (or randomization day if no study drug is received) is Study Day -1; there is no Study Day 0.

For all clinical assessments and procedures performed prior to the date of the first study drug administration, study day will be calculated as the date of the assessment minus the date of the first dose of study drug. For all clinical assessments and procedures performed on or after the date of the first dose of study drug, study day will be calculated as the date of the assessment minus the date of the first dose of study drug, plus 1.

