### **8.7.2 Clinical Laboratory Evaluations**

Central laboratory data will be utilized for all analyses. For the purposes of summarizing post-baseline maximum alkaline phosphatase (ALP), alanine aminotransferase (ALT), aspartate aminotransferase (AST), and total bilirubin and for the purposes of identifying cases of potential Hy's law, both central and local laboratory data will be used. In addition, local laboratory data

will be utilized in the assessment of any Potentially Clinically Significant (PCS) labs as defined in [Appendix B](#). Local laboratory data are collected on the eCRF: 1) if the subject did not meet the laboratory inclusion/exclusion criteria based on the central laboratory results, 2) potential Hy's law is reported based on local laboratory results, and 3) the Principal Investigator chooses to report local laboratory results obtained in the clinical management of the patient.

Laboratory values will be defined as potentially clinically significant (PCS) according to the table in [Appendix B](#). To be considered PCS, the laboratory value must meet both the lower limit and the percent decrease from baseline or both the upper limit and the percent increase from baseline. The proportion of subjects in the Safety Analysis Set with at least 1 PCS laboratory value will be summarized by treatment group and PCS laboratory values will be summarized by treatment group, laboratory parameter, visit and for the overall worst post-baseline value (minimum and maximum value, where appropriate defined in [Appendix C](#)). Percentages for each laboratory test will be based on the number of subjects with a baseline and post-baseline evaluation at the visit for the specific laboratory test. By-subject listings of all laboratory values for a subject with any PCS post-baseline laboratory value will also be provided.

Shift tables will be presented to show the number and percentage of subjects with a laboratory value below the lower limit of normal (LLN), within normal limits, above the upper limit of normal (ULN) and missing at baseline versus the value at each visit and the worst post-baseline value. Percentages for each laboratory test will be based on the number of subjects in the Safety Analysis Set.

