### 8.7.3 ECG Parameters

ECG data are being read centrally. The mean of the triplicates (or if triplicates not available, the duplicates or single ECG, whichever is available) will be used for all analyses, even if not performed within a 5-minute interval. Descriptive statistics for heart rate, PR interval, QRS interval, QT interval, and QT interval corrected by the Fridericia formula (QTcF) and the change from baseline at Day 1 (1-3 hours after the first dose of study drug), Day 4 (inpatients)/96±24h after the first dose of study drug (outpatients) (prior to the first dose of study drug) and Day 4 (1-3 hours after the first dose of study drug) will be summarized by treatment group for subjects in the Safety Analysis Set. In addition, Day 4 post-active dose will be summarized. Change from baseline will be calculated for each subject at Day 1 (1-3 hours after the first dose of study drug) and Day 4 (inpatients)/96±24h after the first dose of study drug (outpatients) (prior to and 1-3 hours after the first dose of study drug) as the value at the specified visit and time point minus the baseline value. The change from baseline to the minimum and maximum post-baseline values will also be summarized by treatment group, where these post-baseline values include unscheduled visits. Change from baseline will be calculated for each subject as the minimum or maximum post-baseline value minus the baseline value. Baseline is defined as the mean of the triplicates from the last assessment prior to the first dose of study drug. ECG parameters for each of the triplicates (including the change in QTcF value from pre-dose to post-dose) and the overall interpretation of the ECG will be presented on a listing.

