### 8.7.4 Vital Signs

Descriptive statistics for temperature, respiratory rate, heart rate, diastolic blood pressure, systolic blood pressure, and the change from baseline at each post-baseline visit will be summarized by treatment group for all subjects in the Safety Analysis Set. Change from baseline will be calculated for each subject at the specified visit as the value at the specified visit minus the baseline value. The change from baseline to the minimum and maximum post-baseline values will also be summarized by treatment group. Change from baseline will be calculated for each subject as the minimum or maximum post-baseline value minus the baseline value. Baseline is defined as the last assessment prior to Day 1.

Post-baseline vital signs will be defined as high or low if the criterion value listed in Table 11 is met. All vital signs will be presented in a listing with a flag for high and low indicating the criterion value was met. PCS is defined as meeting both the criterion value and the change from baseline criterion listed in Table 11. The number and percentage of subjects with any post-baseline PCS vital sign will be presented by treatment group. The overall post-baseline incidence of PCS values, which includes values from unscheduled post-baseline visits, will be summarized by treatment group for the Safety Analysis Set, and all PCS vital sign values will be listed and flagged in by subject listings.

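### SAP 7.2.3 lists the Baseline visit among the values feeding worst post-baseline safety summaries, contradicting its own label and sections 8.7.2 to 8.7.4

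*SAP*

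**What the plan says.** SAP 7.2.3 gives the visit-level rule for overall worst post-baseline analyses. It opens "For overall worst post-baseline analyses (i.e. minimum, maximum, highest, lowest, any post-baseline, and PCS), all assessments including those obtained on unscheduled" visits, and goes on to "scheduled visits (e.g., analysis visits “Baseline”, “Day 1”, “Day 4”, “TOC”, “EOT” and “LFU”) will be included".

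SAP 7.2.1 sets the default that "baseline is defined as the last measurement prior to the first dose of study drug". Vital signs and ECGs have their own versions, and both are meant to be pre-treatment.

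The output sections use different language. For ECGs, SAP 8.7.3 says "The change from baseline to the minimum and maximum post-baseline values will also be summarized by treatment group", adding that these post-baseline values include unscheduled visits; it does not mention Baseline. SAP 8.7.2 (laboratory) and 8.7.4 (vital signs) likewise compute the change as the post-baseline extreme minus the baseline value. The laboratory footnote in Appendix D, on local results, also speaks of worst post-baseline values.

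For PCS, a laboratory value "must meet both the lower limit and the percent decrease from baseline or both the upper limit and the percent increase from baseline" (SAP 8.7.2), and for vital signs "PCS is defined as meeting both the criterion value and the change from baseline criterion listed in Table 11" (SAP 8.7.4). Protocol 9.7 adds: "Treatment-emergent PCS laboratory tests are those in which the Baseline value is not PCS and the post-baseline value is PCS".

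**The concern.** A value taken before the first dose cannot be a post-baseline extreme, yet 7.2.3 is the only place that says which analysis visits feed these summaries, and it names Baseline. Two programmers could build the same table differently, each able to cite the SAP.

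If the list is followed literally, a subject whose values only fall after baseline is given a maximum change of 0 instead of a negative number. A subject whose values only rise is given a minimum change of 0. A subject already over an absolute threshold at entry is counted as over it after treatment. This last case can occur among eligible subjects: on transaminases alone, Protocol 4.2 excludes only "Aspartate aminotransferase (AST) or alanine aminotransferase (ALT) level > 5 times the upper limit of normal (ULN", so someone may enter with ALT between 3 and 5 x ULN, normalise on treatment, and still be counted as having a post-baseline ALT above 3 x ULN.

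QTcF and liver tests matter here. Protocol 1.5.3 reports a Cmax-dependent QTcF prolongation with lefamulin, and potential Hy's Law cases have their own reporting route in Protocol 7.5.

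**Working it through.** The plan states no figure on this point, so there is none to reproduce. The check has three parts.

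**1. Which outputs can a baseline value alter?** A baseline value differs from itself by 0.

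- Laboratory PCS (SAP Appendix B) needs a limit and a percent change; the smallest change required is more than 10% (sodium). 0% fails every row. Not affected.
- Vital-sign PCS (SAP Table 11) needs a criterion value and a change of at least 15 or 20 units. 0 fails every row. Not affected.
- QTcF increase categories (any, >30, >60 msec), and those increases combined with >480 or >500 msec (SAP 8.7.3): 0 is not an increase. Not affected.
- Change to minimum or maximum for laboratory, ECG and vital signs (SAP 8.7.2 to 8.7.4): affected.
- Laboratory shift from baseline to worst value (SAP 8.7.2): affected.
- Absolute QTcF >480 or >500 msec (SAP 8.7.3): affected.
- AST, ALT, bilirubin and ALP multiples of ULN (SAP 8.7.2): affected.

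**2. Change to an extreme.** Let d be the post-baseline maximum minus baseline. Adding Baseline to the pool replaces d by max(d, 0); for the minimum it becomes min(d, 0). If the drug shifts every post-baseline value by the same amount, the mean of max(d, 0) rises by no more than the shift, because subjects with d below 0 contribute nothing until they cross 0. The mean contrast therefore shrinks or stays the same; it does not grow.

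Illustration A. Assumptions, none of them in the documents: baseline and three post-baseline QTcF values independent and normal, each with SD 8/√2 (so each single change has SD 8 ms), and a drug shift of 0 or 10 ms. Simulated means in ms:

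| Output | Pool | Shift 0 | Shift 10 | Contrast |
|---|---|---|---|---|
| Maximum change | Baseline excluded | 4.8 | 14.8 | 10.0 |
| Maximum change | Baseline included | 5.8 | 14.8 | 9.0 |
| Minimum change | Baseline excluded | -4.8 | 5.2 | 10.0 |
| Minimum change | Baseline included | -5.8 | -1.0 | 4.9 |

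(Contrasts are taken before rounding.)

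Illustration B. Assumed within-subject correlation 0.6 and a true shift of 0.30 SD. With Baseline excluded, the contrast in mean maximum change is 0.30 SD. With Baseline included it is 0.24 (three visits, no trend), 0.18 (three visits, values falling 0.5 SD in both arms), 0.17 (one visit, no trend) and 0.10 to 0.11 (one visit, values falling).

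**3. Absolute thresholds.** Let b be the share over the threshold at baseline, equal in both arms by randomisation, and r the post-baseline incidence among the rest. With Baseline included, incidence = b + (1 - b)r. Assume r = 6% and 3%. If no baseline exceedance persists, excluding Baseline gives incidence (1 - b)r and a risk ratio of 2.00 at every b. Including it:

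| b | Incidence, arm 1 | Incidence, arm 2 | Risk ratio | Risk difference |
|---|---|---|---|---|
| 0.5% | 6.47% | 3.485% | 1.86 | 2.985 points |
| 1% | 6.94% | 3.97% | 1.75 | 2.97 points |
| 2% | 7.88% | 4.94% | 1.60 | 2.94 points |
| 5% | 10.70% | 7.85% | 1.36 | 2.85 points |
| 10% | 15.40% | 12.70% | 1.21 | 2.70 points |

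The risk difference is (1 - b)(6% - 3%) with or without Baseline, because b is added to both arms. If every baseline exceedance persists after dosing, those subjects are counted either way and the rule changes nothing.

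**The case against.** The best case against is that this is a drafting slip with no practical force. The sentence is labelled post-baseline, sits under a heading on unscheduled assessments, and serves mainly to bring unscheduled values in. Its visit list is introduced as an example and pools labels across data types: in Appendix D, ECGs have no EOT, TOC or LFU analysis visit and laboratory tests have no Day 1 visit. It is therefore not a parameter-by-parameter specification, and the sections that define the tables all say post-baseline. That reading of the intent is probably right, and it is why the point is an internal contradiction and not a deliberate analysis choice. It does not remove the word, and no other section does.

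A reader might go further and infer that every worst-value output is contaminated, PCS included, since the sentence names PCS. The PCS definitions rule that out, as they do for the QTcF increase categories. Nor can a baseline sample alone meet the combined transaminase and bilirubin criteria in an eligible subject, because Protocol 4.2 excludes that combination.

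A reader might also infer a general dilution of between-arm safety differences, or quote the halving in Illustration A. Neither is supported. Risk differences for threshold counts do not move in the model above. The halving concerns minimum QTcF change, which is not the direction of interest for prolongation; maximum change moves from 10.0 to 9.0 ms. The documents give no SD, drug effect or baseline exceedance rate, and known prolonged QT is an exclusion criterion.

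**Conclusion.** The point holds as an internal contradiction in SAP 7.2.3. Followed literally, the list would let pre-dose values stand as post-baseline extremes in the four kinds of output identified. For change to minimum or maximum, the direction is toward no difference under a common shift; the amount is not determined by the documents, and every figure given for it rests on assumed inputs. For threshold counts, incidence in each arm can rise and the risk ratio can move toward 1, while the risk difference is unchanged provided baseline exceedance is equal between arms. PCS counts, QTcF increase categories and by-visit summaries are unaffected.

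These are descriptive safety tables with no hypothesis test, and no efficacy conclusion depends on them. The point is still worth correcting before database lock, because the affected tables include QTcF and liver extremes and the present text permits two programs.

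**What to change.** In SAP 7.2.3, delete Baseline from the list of scheduled analysis visits and add a sentence that only assessments after the first dose of study drug count toward worst post-baseline summaries.

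- **Laboratory and ECG:** apply it by date and time. For laboratory tests this also settles pre-dose local results, which Appendix D bars from the Baseline visit but admits under the Unscheduled label and into worst-value identification.
- **Vital signs:** SAP 7.2.1 notes that assessment time is not captured, so a date- or visit-based rule is needed. It should say explicitly how Day 1 is handled, because schedule footnote b places Day 1 assessments before dosing while footnote i asks for the vital signs at the highest temperature after the first dose.

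The cost is one deleted word, one added sentence and a short vital-sign rule, made by SAP amendment before lock. No new data are needed, and the PCS definitions and efficacy analyses stay as they are.

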### 7.3 Randomization

Subjects will be assigned to receive lefamulin or moxifloxacin in a 1:1 ratio with stratification by geographic region (US vs. ex-US), receipt of prior single dose short-acting antibiotic therapy for CABP vs. none, and PORT risk class (II vs. III/IV) using blocked randomization via the IRT. The randomization schedule will be generated by the Sponsor (or designee). Subjects randomized into the study will be assigned the treatment corresponding to the next available number in the respective stratum of the computer-generated randomization schedule. The subject will only be randomized after the inclusion and exclusion criteria are verified.

The Sponsor designee (ie, IRT vendor) will maintain the randomization codes in accordance with standard operating procedures to ensure the blind is properly maintained, and that only Sponsor personnel who require knowledge of treatment assignments will be unblinded (eg, staff involved in maintaining the clinical supplies or SAE reporting). After the database is locked and the SAP is final, the study blind codes will be broken.

